6.2 Analysis of Endpoints

Primary Endpoints:

1. Opioid utilization for the first 24 hours after surgery, including during surgery, calculated as oral morphine equivalent.

CONFIDENTIAL

This material is the property of the NYU School of Medicine and Langone Medical Center. Do not disclose or use except as authorized in writing by the study sponsor

Secondary Endpoints:

1. Patient reported VAS scores in PACU
2. Length of stay in PACU
3. Patient reported VAS scores on POD 1, POD 2, POD 3, POD7
4. Reaction to IPACK block
5. Mid-term functional outcomes will be assessed at 6 months: VAS, KOOS-PS, KUJALA, Tegner Activity Scale, strength, ROM.

Normally distributed data such as the primary outcome variable will be compared using the two-sample t-test. In the case that the data are not normally distributed, the Wilcoxon rank-sum test will be used instead. Categorical variable will be compared using the Chi-Squares unless other tests such as the Fisher's exact test are more appropriate.

All endpoints will be evaluated as fits the data set with graphical figures such as scatter plots, box-and-whisker plots, and frequency histograms to visualize the distribution of these outcomes and their relationships to covariates and treatment assignment. When appropriate descriptive graphical and tabular methods will also be estimated and presented in a graphical figure.

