Endpoint	Primary Endpoint: Opioid utilization for the first 72 hours after surgery, including during surgery, calculated as morphine equivalent. Secondary Endpoints: Opioid consumption Post-operatively Patient reported VAS scores in PACU Length of stay in PACU Patient reported VAS scores on POD 1, POD 2, POD 3, POD 7 Reaction to IPACK block Incidence of postoperative complications
Study Duration	The study will continue until 50 subjects are enrolled per arm, to allow for potential dropout and increased power.
Participant Duration	Each participant will be enrolled on DOS and complete their final follow up on postoperative day seven.
Duration of IP administration	Once during surgery
Population	50 patients per study arm scheduled for ACLR with BPTB autograft
Study Sites	NYU Langone Orthopedic Hospital and NYU Ambulatory Surgery Center at 38 th street
Number of participants	100
Description of Study Agent/Procedure	Patients in both the study and control group will receive the standard of care adductor canal block composed of 15 mL of Bupivacaine (0.25%). Patients in the study group will receive the additional IPACK block performed using 20 mL of Bupivacaine (0.25%) injected into the interspace between the popliteal artery and capsule of the knee. Patients will be blinded to their group allocation.
Reference Therapy	Reference is isolated adductor canal block
Key Procedures	Adductor canal block 15 mL 0.25% Bupivacaine, IPACK block with 20 mL 0.25% bupivacaine

CONFIDENTIAL

This material is the property of the NYU School of Medicine and Langone Medical Center. Do not disclose or use except as authorized in writing by the study sponsor

Statistical Analysis	Continuous and categorical baseline characteristics will be compared using Hedges standardized difference. Normally distributed data will be compared using t tests while non-normally distributed continuous outcomes will be assessed using the Mann-Whitney U test.
----------------------	--

CONFIDENTIAL

This material is the property of the NYU School of Medicine and Langone Medical Center. Do not disclose or use except as authorized in writing by the study sponsor

1 Background and Specific Aims

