1.2 Statistical Hypothesis

We hypothesize that patients who receive an IPACK block plus an ACB will have lower postoperative opioid consumption over the first 24 hours (measured in morphine equivalents) compared to those who an isolated ACB following anterior cruciate ligament reconstruction. Furthermore, the study group will report lower postoperative pain scores on POD1 than the control group. Failing to reject the null would signify that the IPACK block has no clinically relevant difference on post-operative opioid consumption outcomes following ACLR with BPTB autograft.

CONFIDENTIAL

This material is the property of the NYU School of Medicine and Langone Medical Center. Do not disclose or use except as authorized in writing by the study sponsor

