1.3 Objectives and Purpose

The goal of this study is to determine if the addition of IPACK block to the standard of care adductor canal block is superior to an isolated adductor canal block in decreasing postoperative pain, decreasing opioid consumption, and leads to increased duration of analgesia in patients undergoing ACLR. The primary objective will be to compare opioid utilization between the two arms within the first 72 hours after surgery, including intraoperatively, as measured by morphine equivalents. Our secondary objectives are measuring patient reported pain scores in PACU at 24 hours, 48 hours, and 72 hours, and at the first postoperative visit (POD 7).

2 Study Design and Endpoints

Arm 1: Experimental	Arm 2: Control
Sample Size: 50	Sample Size: 50
Medication: 15 mL of 0.25% Bupivacaine block of the saphenous nerve injected under ultrasound guidance via adductor canal and IPACK block with 20 mL of 0.25% Bupivacaine injected into the Interspace between the Popliteal Artery and Capsule of the Knee	Medication: 15 mL of 0.25% Bupivacaine block of the saphenous nerve injected under ultrasound guidance via adductor canal

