4.2.3 Follow-Up Phone call/message (POD 1, POD 2 and POD 3)

Phone call to patient to collect additional data on opioid use following discharge, on POD 1, POD 2 and 3 after surgery

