6.1 General Approach

The primary analysis will follow the intention-to-treat (ITT) principle in order to evaluate the true outcome of the intervention as experienced by the patient who is blinded to the intervention.

Continuous and categorical baseline characteristics will be compared using Hedges standardized difference. Normally distributed data will be compared using t tests while non-normally distributed continuous outcomes will be assessed using the Mann-Whitney U test.

It is anticipated that the data for some subjects will be incomplete for various reasons: missing diary entries, refusal to answer a question on the questionnaire, onset of illness, loss-to-follow-up, etc. All occurrences of incomplete data will be investigated to carefully document the reasons for the missing data. If the primary outcome (amount of opioid utilization for the first 24 hours after surgery) cannot be ascertained with a reasonable degree of certainty, the patient will be excluded from the study.

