6.3 Sample Size

Using a 2-sided, 2-sample t test, an α value of 0.05, a power analysis revealed that 42 subjects were needed per group to detect a moderate effect size with a power of 0.80. We chose to enroll 50 subjects per arm to allow for potential dropout and an increased power.

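### The primary endpoint is 72-hour opioid use in the Summary and primary objective but 24-hour use in the hypothesis, the missing-data rule and the analysis section, and nothing says which governs

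*Combined protocol and SAP*

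**What the plan says.** Five places define or use the primary measure.

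**72 hours**
- Protocol Summary, Endpoint row: "Primary Endpoint: Opioid utilization for the first 72 hours after surgery, including during surgery, calculated as morphine equivalent".
- Section 1.3, primary objective: to "compare opioid utilization between the two arms within the first 72 hours after surgery, including intraoperatively".

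**24 hours**
- Section 1.2, hypothesis: "lower postoperative opioid consumption over the first 24 hours (measured in morphine equivalents".
- Section 6.1, missing-data rule, where the primary outcome is glossed as "amount of opioid utilization for the first 24 hours after surgery". A patient for whom this cannot be established is excluded.
- Section 6.2, the only listed primary endpoint: "Opioid utilization for the first 24 hours after surgery, including during surgery, calculated as oral morphine equivalent".

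Three other places might have settled the matter and do not.
- The Summary's secondary list opens with "Secondary Endpoints: Opioid consumption Post-operatively", with no hours attached. The secondary list in 6.2 has no opioid item.
- Section 6.3 says that "42 subjects were needed per group to detect a moderate effect size with a power of 0.80". It names no endpoint, window, SD or difference.
- Section 4.2.3 schedules a "Phone call to patient to collect additional data on opioid use following discharge, on POD 1, POD 2 and 3 after surgery", so the data support either window.

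**The concern.** A primary endpoint is fixed in advance so that the confirmatory result cannot be chosen after the data are seen. Here an author could report either the 24-hour or the 72-hour comparison and cite the protocol for it. The two can disagree, because adding days 2 and 3 changes both the expected difference and the variance. How far they disagree depends on how long the effect of the block lasts.

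The exclusion rule is also affected. It is written for 24-hour data. If 72 hours governs, a patient with a known 24-hour total but missing day 2 or day 3 data stays in the study without a primary outcome value, and no rule covers that case. Section 6.1 itself anticipates missing diary entries and loss to follow-up.

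A smaller mismatch sits alongside. Section 1.2 speaks of postoperative consumption only, whereas the Summary, 1.3 and 6.2 all count opioids given during surgery.

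**Working it through.** **1. The text, side by side**

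| Place | Window | Intraoperative use |
|---|---|---|
| Protocol Summary, primary endpoint | 72 h | counted |
| 1.3, primary objective | 72 h | counted |
| 1.2, hypothesis | 24 h | worded as postoperative |
| 6.1, exclusion rule | 24 h | not mentioned |
| 6.2, primary endpoint | 24 h | counted |

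Each window appears in more than one operative section, so this is not a single slip. No order of precedence is stated. The finding needs no arithmetic; what follows only illustrates the consequence.

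**2. The plan's own sample-size figure**

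Inputs from 6.3: two-sided two-sample t test, α = 0.05, power 0.80, 42 per group, 50 enrolled per arm. The moderate effect is not given a number, so 42 cannot be reproduced directly. Solving the noncentral-t power equation for the effect at 42 per group gives 0.619 SD. For comparison, 0.5 SD would need 64 per group. At 50 per arm, power is 0.865 for 0.619 SD and 0.697 for 0.5 SD. Section 6.3 does not say which window these figures belong to.

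**3. Type I error if either window may be claimed**

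Assume both totals are tested at two-sided 0.05, with correlation ρ between the test statistics. Then the error is 1 − P(|Z₁| < 1.96 and |Z₂| < 1.96) under a bivariate normal distribution.

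| Assumed ρ | Type I error |
|---|---|
| 0.577 | 0.088 |
| 0.7 | 0.083 |
| 0.8 | 0.078 |
| 0.9 | 0.070 |

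The plan does not propose this double testing. The table shows what an open choice would allow.

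**4. Power for the 72-hour total at 50 per arm**

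Assumptions: day 1 has SD 1, days 2 and 3 each have SD s, every pair of days has correlation r, and the day-1 effect is 0.619 SD. The variance of the 72-hour total is

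1 + 2s² + 2r(2s + s²).

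If the effect is confined to day 1, the standardized effect on the total is 0.619 divided by the square root of that variance. If the same standardized effect holds on each day, it is 0.619(1 + 2s) divided by that square root.

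| s | r | Variance | Day-1-only effect (SD) | Power | Persistent-effect power |
|---|---|---|---|---|---|
| 1 | 0 | 3.0 | 0.619/1.732 = 0.357 | 0.424 | >0.99 |
| 1 | 0.8 | 7.8 | 0.619/2.793 = 0.222 | 0.195 | 0.908 |
| 0.5 | 0 | 1.5 | 0.619/1.225 = 0.505 | 0.706 | 0.999 |
| 0.5 | 0.8 | 3.5 | 0.619/1.871 = 0.331 | 0.374 | 0.906 |

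Against 0.865 for the 24-hour total, the 72-hour window is much weaker if the benefit ends with day 1 and stronger if it persists. The windows are not interchangeable, and which one is favourable depends on facts that the data will reveal.

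**The case against.** The best defence is that the statistical section is consistent with itself. Sections 6.1 and 6.2 both use 24 hours, and so does the only stated hypothesis, so an analyst working from section 6 alone would have one primary endpoint. That favours 24 hours but does not settle it. The Summary and 1.3 are just as explicit, 1.3 labels the 72-hour comparison the primary objective, and nothing gives section 6 precedence.

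A second objection is that the figures rest on assumptions. That is true. No SD, effect or correlation is in the documents, and the type I error arises only if both windows are tested and either may be claimed. The top of that range corresponds to equal daily SDs with no correlation between a patient's days, which is an extreme case. The correlations implied by the power model reach 0.96, where the error is about 6.3%, so the inflation could be smaller than the quoted range. None of this touches the contradiction.

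A third objection concerns the repair. If 72 hours is chosen and the 6.1 exclusion rule is moved with it, more randomised patients could be excluded, although 6.1 and 3.6 promise intention-to-treat. That caution is fair. The tension between excluding patients and intention-to-treat already exists at 24 hours, however, and is no reason to leave the window undefined.

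**Conclusion.** The concern holds and must be fixed. Two places set the primary measure at 72 hours, three use 24 hours, and nothing ranks them. This conclusion rests on the text alone and is held with high confidence. The documents do not show which window was intended.

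The size is illustrative. Type I error would be about 7.0% to 8.8% against a nominal 5% if either window could be claimed, for assumed correlations of 0.9 to 0.58. With an assumed 0.62 SD effect confined to day 1 and inter-day correlation of 0 to 0.8, 72-hour power at 50 per arm is 42% to 20% with equal daily SDs. It is 71% to 37% if the SDs of days 2 and 3 are half that of day 1. The 24-hour total has 86%. If the same standardized effect lasts all three days, 72-hour power is about 91% or more.

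**What to change.** Before any outcome is compared by arm:

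1. Name one primary window and state it identically in the Summary, 1.2, 1.3, 6.1 (including the exclusion rule) and 6.2. Choosing 24 hours changes the window in two places (Summary and 1.3). Choosing 72 hours changes it in three (1.2, 6.1 and 6.2).
2. List the other window, with its hours, as a secondary endpoint in both the Summary and 6.2.
3. Bring 1.2 into line with the other definitions on opioids given during surgery.
4. Name the chosen window in 6.3 as well, so that the power statement belongs to a defined endpoint.
5. If 72 hours is chosen, say how a patient with missing day 2 or day 3 data is handled, consistently with intention-to-treat.

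The cost is a wording amendment, which under section 10.2 needs IRB approval before it takes effect. It needs no additional data collection. It needs no additional patients either, provided the sponsor keeps 50 per arm; re-justifying power for a 72-hour endpoint would be a separate decision. The price is that only one window carries the confirmatory claim.

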12.1	FUNDING SOURCE.....	25
12.2	COSTS TO THE PARTICIPANT	25
12.3	PARTICIPANT REIMBURSEMENTS OR PAYMENTS	25
13	CONFLICT OF INTEREST POLICY.....	25
14	REFERENCES	26
15	ATTACHMENTS	27
15.1	OPIOID EQUIVALENTS.....	27
15.2	BASELINE ASSESSMENTS.....	ERROR! BOOKMARK NOT DEFINED.
15.3	MEDICATION USAGE RECORD	ERROR! BOOKMARK NOT DEFINED.

CONFIDENTIAL

This material is the property of the NYU School of Medicine and Langone Medical Center. Do not disclose or use except as authorized in writing by the study sponsor

List of Abbreviations

ACLR	Anterior Cruciate Ligament Reconstruction
BPTB	Bone Patellar Tendon Bone
IPACK	Interspace between the Popliteal Artery and Capsule of the Knee
ACB	Adductor Canal Block
ASA	American Society of Anesthesiologist Score
BMI	Body Mass Index
DOS	Day of surgery
VAS	Visual analog scale
AE	Adverse event
SAE	Serious adverse event
IV	Intravenous
ITT	Intention-to-treat
PACU	Post-Anesthesia Care Unit
PO	Taken orally
CI	Confidence interval
SD	Standard deviation; a parameter that characterizes a population distribution
SE	Standard error
ANOVA	Analysis of variance; a linear model
NSAID	Non-steroidal anti-inflammatory drug

CONFIDENTIAL

This material is the property of the NYU School of Medicine and Langone Medical Center. Do not disclose or use except as authorized in writing by the study sponsor

Protocol Summary

Title	Adductor Canal Block and IPACK Block vs. Isolated Adductor Canal Block for Post-Operative Analgesia Following ACL Reconstruction with Bone Patellar Tendon Bone Autograft: A Single Center Randomized Placebo-Controlled Trial.
Brief Summary	A randomized, single-blind, single-center study measuring the effects of adductor canal block combined with IPACK infiltration compared to adductor canal block alone on post-operative pain and opioid consumption in patients undergoing ACL reconstruction with Bone Patellar Tendon Bone Autograft
Objectives	To determine if the addition of an IPACK block to the standard adductor canal block is superior to an isolated adductor canal block in controlling post-operative pain and decreasing postoperative opioid consumption in patients undergoing ACLR with Bone Patellar Tendon Bone Autograft
Methodology	Randomized, single-blind, single-center study

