2.1 Description of Study Design

RECRUITMENT PHASE/CONSENTING PHASE:

Surgeons will identify eligible patients via Epic during their initial clinic visit and discuss the study. Surgeons will provide research coordinator with the name and medical record number of eligible patients. If the patient meets the inclusion criteria outlined below and is agreeable, subjects will be first introduced to the study during one of their presurgical clinic visits and then consented on the day of surgery by a member of the research team. Patients will be made acquainted with the study prior to surgery. On DOS when they arrive 1.5/2 hours before surgery, we (study team members) will consent them in a private room and provide ample time to discuss and review any questions or concerns they may have.

BASELINE ASSESSMENTS:

Subjects will complete a baseline VAS McGill Pain scale, Kujala, KOOS-PS and Tegner Activity Scale

RANDOMIZATION PHASE:

Subjects scheduled to undergo ACLR with BPTB autograft will be randomized to either ACB with IPACK block or to ACB only. A randomization scheme will be created prior to start of study enrollment using the randomizer.org website to generate the assignment. Block randomization is commonly used in clinical trial design to reduce bias and achieve balance in the allocation of participants to treatment arms throughout the course of the study. Randomized block design allows us to account for variables so that observed differences are largely due to true differences between treatments and not to the variable. We will create blocks of four patients and in each block, two patients will be assigned to the IPACK + ACB group, and two to the ACB only

CONFIDENTIAL

This material is the property of the NYU School of Medicine and Langone Medical Center. Do not disclose or use except as authorized in writing by the study sponsor

group. Thus, patients in both groups will be evenly spread from the beginning to the end of the study.

A research coordinator will place the randomization results in sealed envelopes prior to recruitment. Each subject enrolled in the study will be assigned a number and the sealed envelope assigning the subject to the IPACK + ACB or ACB only will be opened on the day of surgery after the patient has signed consent agreeing to participate in the study.

Patients will be blinded to their group allocation. During peripheral block patients are sedated and postoperatively, the areas of infiltration will be covered by bandage.

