TREATMENT PHASE:

Patients in both the study and control group will receive the standard of care adductor canal block. This consists of 15mL of bupivacaine (0.25%) Injected under ultrasound guidance in the saphenous nerve via the adductor canal. Patients in the study group will receive the additional IPACK block performed using 20 mL of bupivacaine (0.25%) injected into the interspace between the popliteal artery and capsule of the knee.

[figure not shown]
POST-OPERATIVE PHASE:

After initial recruitment, subjects' pain will be assessed via visual analog scale (VAS) by nursing staff during the post-operative period as per standard of care in the post anesthesia care unit, and by the research staff prior to leaving the surgical center. The VAS pain scores are collected and documented in the patient's electronic medical record. Additionally, a standardized regimen of pain medication will be given to all subjects who are enrolled. The pain medications given to patients are standard of care medication 325-5 mg Percocet and vary based on pain level. This is determined by the clinical staff caring for each patient. While the patient is in the PACU prior to discharge, an authorized research member will visit the patient and obtain a pain score using the VAS and McGill Pain Scale. Data on PACU opioid use documented in the electronic medical record will be collected. On POD1, POD 2 and POD 3, a phone call or email survey will be sent to the patient to collect additional data on opioid use at home as well as a VAS score at 24, 48, and 72 hours after surgery.

CONFIDENTIAL

This material is the property of the NYU School of Medicine and Langone Medical Center. Do not disclose or use except as authorized in writing by the study sponsor

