6.4 Enrollment/Randomization/Masking Procedures

We will utilize randomization.com to generate a block randomization assignments for all 100 participants. Someone that is not a stakeholder in the study will make randomization envelopes, which include the study ID number, the treatment assignment, and dosage specifics. These randomization envelopes will then be distributed to the anesthesiologist pre-operatively by the authorized researcher after informed consent is obtained.

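### The primary endpoint counts opioid given during surgery, but no readable text sets a rule for giving it, and the anesthesiologist has the assignment beforehand

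*Combined protocol and SAP*

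**What the plan says.** Every full statement of the primary endpoint includes opioid given during surgery. Section 6.2 has "Opioid utilization for the first 24 hours after surgery, including during surgery, calculated as oral morphine equivalent". The Protocol Summary has "Opioid utilization for the first 72 hours after surgery, including during surgery, calculated as morphine equivalent", and section 1.3 has "within the first 72 hours after surgery, including intraoperatively, as measured by morphine equivalents". The 24 h and 72 h windows conflict, but that is a separate matter; the intraoperative part is in both.

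On dosing, section 2.1 promises a standardized pain regimen for all enrolled subjects. That sentence stands under the post-operative phase, and the content given is: "The pain medications given to patients are standard of care medication 325-5 mg Percocet and vary based on pain level". The clinical staff looking after the patient decide. The treatment phase in 2.1, the procedures in 4.1.1, the day-of-surgery list in 4.2.2 and the concomitant medication section 4.3 give no rule for opioid during surgery.

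On blinding, the Protocol Summary describes a "randomized, single-blind, single-center study", and section 2.1 says: "Patients will be blinded to their group allocation". Section 6.4 says of the envelopes, which hold the treatment assignment: "These randomization envelopes will then be distributed to the anesthesiologist pre-operatively by the authorized researcher after informed consent is obtained". Section 5.1 has an anesthesiologist perform both blocks. The arm table in section 2 gives the control arm the adductor canal block alone, with no sham IPACK, although the title calls the trial placebo-controlled.

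The Protocol Summary also lists a secondary endpoint, "Opioid consumption Post-operatively". Section 6.2 omits it.

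**The concern.** Part of the primary endpoint is a clinician's dosing decision, and the clinician who makes it may know the arm. Blinding the patient gives little protection during surgery, when the patient is not asking for analgesia. Section 4.1.2 describes IPACK as an accepted component of multimodal analgesia for this operation, so a clinician could reasonably expect it to work and give less opioid for that reason alone.

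Randomisation does not remove a difference in dosing that arises after allocation. Once intraoperative, PACU and home opioid are added into one total, such a difference cannot be told apart from an effect of the block. As section 6.2 stands, no planned analysis would show a reader whether the result depends on the intraoperative part.

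**Working it through.** **Step 1: is there a rule for intraoperative opioid?** Section by section:

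| Place | What it gives on intraoperative opioid |
|---|---|
| 2.1, treatment phase | Local anesthetic volumes only |
| 2.1, post-operative phase | Oral Percocet, varied by pain level; nothing during surgery |
| 4.1.1 | Blocks, pain scores and PACU opioid data |
| 4.2.2 | Opioid usage is recorded; no rule for giving it |
| 4.3 | Concomitant medications are recorded on the CRF; no rule |
| 3.4, chart abstraction | Names opioid in the PACU only |

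A figure in 2.1, the schematic in 2.2 and the Manual of Procedures mentioned in 11.3 could not be read. The supportable statement is that no readable text gives a rule.

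**Step 2: who knows the arm?** An anesthesiologist gets the envelope (6.4) and an anesthesiologist performs the blocks (5.1). The block provider must know the arm. The documents do not say whether that person also gives the intraoperative opioid, or how much is usually given.

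**Step 3: how large could it be?** The plan has no figure on this point to reproduce, so this is an illustration.

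Inputs from the documents:
- two-sided two-sample t test, α = 0.05 (6.3)
- 50 per arm (6.3)
- factor 150 for IV fentanyl and 1.5 for oral oxycodone (table 15.1)

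Assumed inputs:
- fentanyl as the agent
- a mean arm difference of 0.05 mg
- an endpoint SD of 20 to 60 mg OME (the documents give none)
- no true block effect

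Conversion: 0.05 mg × 150 = 7.5 mg OME, the same as one 5 mg oxycodone tablet (5 × 1.5 = 7.5). If greater later use offsets half of this (also assumed), the net shift is 7.5 × 0.5 = 3.75 mg OME.

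Standardised shift d = shift / SD. Noncentrality = d × √(50/2) = 5d, with 98 degrees of freedom. The chance of p<0.05 comes from the noncentral t distribution.

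| Net shift (mg OME) | SD (mg) | d | Noncentrality | Chance of p<0.05 |
|---|---|---|---|---|
| 7.5 | 60 | 0.125 | 0.625 | 9.5% |
| 7.5 | 40 | 0.188 | 0.938 | 15.3% |
| 7.5 | 20 | 0.375 | 1.875 | 45.9% |
| 3.75 | 60 | 0.063 | 0.312 | 6.1% |
| 3.75 | 40 | 0.094 | 0.469 | 7.5% |
| 3.75 | 20 | 0.188 | 0.938 | 15.3% |
| 0 | any | 0 | 0 | 5.0% |

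A larger SD, which a 72 h total might have, dilutes the shift. The 45.9% needs both the smallest assumed SD and a full shift with no offset, so it lies at the top of the illustration.

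**The case against.** The mechanism is inferred. Nothing says that the person who places the block also gives the intraoperative opioid, or that anyone would dose by arm. The unread figure, schematic or Manual may hold a rule. All of this stands, and it limits the point to a possibility.

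The shift may also be partly self-correcting. If a patient in the IPACK arm gets less opioid in surgery and the block does nothing, that blinded patient may need more in PACU or at home, and the same endpoint counts it. This stands too, and is why the half-offset rows belong beside the full ones.

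Lower intraoperative opioid could be a true benefit of a working block. Agreed; dropping it from the primary endpoint would be wrong.

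Data capture is largely provided for. Sections 4.2.2 and 4.3 already require opioid usage and concomitant medications to be recorded, so a reader should not infer from the abstraction list in 3.4 that intraoperative opioid would go unrecorded. That list is merely incomplete.

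The promise of a standardized regimen in 2.1 is the nearest counter-evidence. It does not answer the point, because it is postoperative, names only oral Percocet and leaves dosing to clinical staff.

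**Conclusion.** The point holds as a cheap improvement. A component of the primary endpoint has no readable dosing rule and may be set by someone who knows the arm, and 6.2 plans nothing that would reveal the consequence.

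A reader might infer that the primary comparison is biased in favour of IPACK, or that its false-positive rate is 46%. The documents support neither. The doser's identity, any difference in dosing, its direction and its size are all unstated. The range of about 10–46% rests on an assumed agent, an assumed 7.5 mg OME shift, assumed SDs of 60 to 20 mg and no later offset. With half offset it is about 6–15%, and with no differential dosing the rate is the nominal 5%. Nor does the point require the block provider to be blinded, which is not feasible. What is lacking is a common rule and a breakdown by period.

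**What to change.** (a) In section 2.1, require that intraoperative opioid in both arms follow one common order set, with agent, dose and trigger chosen by the clinicians and fixed before enrolment, and with departures allowed but recorded. Add intraoperative opioid (mg) to the chart abstraction list in 3.4. If a rule already exists in material not seen here, citing it in 2.1 is enough.

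(b) In section 6.2, restore the secondary endpoint from the Protocol Summary as postoperative OME from PACU arrival to the end of the primary window, excluding opioid given during surgery. The 24 h/72 h conflict must be settled first so that the window is defined. Report OME by arm for the intraoperative, PACU and post-discharge periods.

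(c) State in 6.2 that these are supporting analyses and are not free of bias. Less intraoperative opioid in the IPACK arm could raise later use and so bias postoperative OME against IPACK. The clinical staff who set PACU dosing are also not stated to be blinded.

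The primary endpoint and the sample size are unchanged. The cost is a shared order set, a few sentences, one restored endpoint and one extra table. The downside is slightly less latitude for the anesthesiologist. An order set that permits departures reduces discretion without removing it, which is why the departures need recording.
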